Maintenance of Compliance :- Compliance with treatment protocol will be emphasized from time to time. To aim at a high level of compliance for both groups, we will explain to the patients and their legal guardians in details about the purposes of the study. Rapport is emphasized. Our RA will make regular phone contacts with the subjects of both groups to provide support and enquire about their situation, indicate concerns about their difficulties, answer any queries and remind them of the importance of adherence to the treatment protocol. We will also engage active participation of the parents. With experiences from previous clinical trials involving adolescent scoliosis subjects [22], we are confident that subjects will be compliant with the study protocol.

Persistence of study in COVID-19 pandemic environment:-

Research investigations are done during routine clinic visits. Since AIS subjects will need to come back for follow-up of their scoliosis even during a pandemic, this study will persist and not be affected even under the COVID-19 or other infection disease pandemic environment.

Statistical Analysis:-

The spread of data will be tested for normality. For data that is normally distributed, the numerical data are expressed as mean \pm SD. Otherwise they are expressed as median (interquartile range). Demographic data, anthropometric data, QoL scores, initial Cobb angle and other curve morphological data between the two groups at baseline will be compared using two-sided independent student's t-test or Chi-square test as appropriate.

To analyze treatment outcomes, the “Intention-to-Treat” approach is adopted. For the primary objective, two-sided independent student's t-test will be used to compare between-group IBC. For secondary objectives, Chi-square test will be used for comparing the proportions of successful treatment between the two groups. Logistic regression and linear regression model will be used for control of confounding from brace compliance and variables that are unbalanced at baseline between the study groups. QoL scores at the 18-month time-point for the two study groups will be compared with ANCOVA for adjustment of effect from baseline QoL scores. A p value of < 0.05 is considered statistically significant. SPSS 20.0 for Windows will be used for statistical analysis.

[figure not shown]
Sample size estimation:-

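### Covariates for the logistic and linear models are chosen by chance baseline imbalance, so known prognostic variables would usually be left out

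*Protocol*

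**What the plan says.** All of this is in the protocol, section (b)(i), under Statistical Analysis.

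- **Baseline comparison.** "Demographic data, anthropometric data, QoL scores, initial Cobb angle and other curve morphological data" are to be compared between the arms by t-test or Chi-square test ("between the two groups at baseline will be compared using two-sided independent student's t-test or Chi-square test as appropriate").
- **Covariates of the regression models.** "Logistic regression and linear regression model will be used for control of confounding from brace compliance", and the same sentence adds "variables that are unbalanced at baseline between the study groups". No baseline variable is named, imbalance is given no definition or threshold, and the sentence does not tie the models to particular outcomes.
- **Analyses outside this rule.** For the primary objective, "two-sided independent student's t-test will be used to compare between-group IBC". Treatment success is compared by Chi-square test. Quality-of-life scores at 18 months are "compared with ANCOVA for adjustment of effect from baseline QoL scores", so there the covariate is fixed in advance.
- **Significance level.** "A p value of < 0.05 is considered statistically significant" is the only threshold stated in the section.

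Under Subject Randomization, allocation is randomised and stratified in permuted blocks of 10. The stratification factors are not named.

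**The concern.** Randomisation makes any baseline difference between the arms a matter of chance. A rule that adjusts only for what turns out unbalanced therefore picks covariates by luck. Whether a variable predicts the outcome plays no part.

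This matters most where the starting value plainly bears on the result. Entry Cobb angle runs from 20° to 40°, and two of the success criteria are absolute limits at maturity (45° and 55°). Under the rule, initial Cobb angle enters the model only if chance happens to unbalance it. If it was a stratification factor it would be balanced by design and would enter even more rarely.

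At stake are the precision that fixed adjustment would bring, protection against moderate imbalance in a strong predictor, and a model whose content does not depend on chance or on someone's later reading of an undefined word.

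**Working it through.** **1. Sample size, to set the scale.** The rule has no figure of its own, so the planned sample size was reproduced first. Inputs from Sample size estimation: effect 0.8 SD, alpha 0.025, power 0.95.

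n per arm = 2(z₀.₉₈₇₅ + z₀.₉₅)²/0.8² = 2(2.241 + 1.645)²/0.64 = 47.2, so 48. The exact t calculation gives 49, the protocol's figure, with alpha read as two-sided. With 60 per arm and 20% dropout, 60 × 0.80 = 48 are evaluable.

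**2. How often a given variable is selected.** Under randomisation a baseline p-value falls below a cut-off *a* with probability *a*, so the variable is left out with probability 1 − a.

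- Cut-off 0.05: left out in 95% of trials
- Cut-off 0.10: 90%
- Cut-off 0.20: 80%

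The chance that at least one of k independent variables is flagged at 0.05 is 1 − 0.95^k: 23% (k = 5), 40% (k = 10), 54% (k = 15). Related variables lower this. With assumed within-group correlations of 0.7 and 0.5 among 15 variables it is about 46%.

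**3. Precision for a continuous outcome.** Assumptions: true effect 0.5 SD, 48 per arm, one prognostic covariate with correlation ρ to the outcome (no document gives ρ), two-sided 5% test, selection at p < 0.05.

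SE = √(2/n) × √(1 − ρ²) when the covariate is always entered:

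- Unadjusted: √(2/48) = 0.204; power ≈ Φ(0.5/0.204 − 1.96) ≈ 69%
- ρ = 0.3: 0.204 × 0.954 = 0.195; power ≈ 73%
- ρ = 0.5: 0.204 × 0.866 = 0.177; power ≈ 81%

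Simulation, which uses the t distribution, gives slightly lower values for the same set-up:

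| Setting | Unadjusted | Imbalance rule | Covariate fixed |
|---|---|---|---|
| 48 per arm, 15 variables screened, ρ = 0.3 | 68% | 66% | 71% |
| 48 per arm, 15 variables screened, ρ = 0.5 | 68% | 66–67% | 79–80% |
| 49 per arm, only the prognostic variable screened, ρ = 0.3 | 69% | 69% | 72% |
| 49 per arm, only the prognostic variable screened, ρ = 0.5 | 69% | 70% | 81% |

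The rule recovers almost none of the available gain. Screening many variables can cost a little power, because a flagged variable with no prognostic value is correlated with treatment and widens the standard error.

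At the planned 0.8 SD (49 per arm), power is 98% under the rule against 98% (ρ = 0.3) and 99% (ρ = 0.5) with the covariate fixed.

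**4. Type I error.** With 49 per arm, size at nominal 5% is 4.9% (ρ = 0.3) and 4.2% (ρ = 0.5) under the rule, so it is slightly conservative overall. At ρ = 0.5 this average breaks down as follows:

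- Covariate baseline p between 0.05 and 0.20 (15% of trials, covariate omitted): about 9%
- Baseline p above 0.20 (80% of trials, covariate omitted): about 3.4%
- Baseline p below 0.05 (5% of trials, covariate entered): about 5%

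Check: 0.15 × 9% + 0.80 × 3.4% + 0.05 × 5% ≈ 4.3%.

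**5. Binary treatment success.** Logistic simulation with an assumed latent shift of 0.6 SD, power under the rule against fixed adjustment:

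- 48 per arm: 61% v 64% (ρ = 0.3); 62% v 69% (ρ = 0.5)
- 25 per arm (an assumed number of completers): 37% v 38%; 38% v 41%

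A second logistic simulation, with an assumed treatment log-odds of 1.2 and covariate log-odds of 1.0 per SD, gave 60% v 66%.

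**The case against.** The strongest case on the other side is that the rule touches only supportive analyses and that its cost depends on assumptions. Most of this stands.

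- **The trigger is inferred.** A reader might take p < 0.05 as the protocol's definition of imbalance. It is the only threshold stated, but the text never links it to covariate selection, and an analysis plan not shown here could define the term. The conclusion survives, because any definition based on observed imbalance still selects by chance.
- **The primary result is not affected.** A reader might infer that the in-brace correction comparison is at risk. The named primary test is an unadjusted t-test and the quality-of-life ANCOVA has a fixed covariate; neither uses the rule.
- **False positives are not inflated.** The rate of about 9% applies to a selected 15% of trials and is offset elsewhere. It shows that moderate imbalance goes unadjusted, not that the overall test is invalid.
- **Crude and adjusted results need not compete.** The protocol already names the main test for each objective. The selection uses baseline data only, not outcomes.
- **The correlations are unsupported.** Entry limits on Cobb angle, Risser stage and menarchal status narrow these covariates, and in-brace correction is already divided by pre-brace Cobb angle. Correlations as high as 0.7, which would make the loss look dramatic, have no basis in the document and are not relied on.
- **The binary outcome gains less.** In this 3-year phase curve progression is assessed only in those who have completed bracing or need surgery, so numbers may be small.

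What does not stand is the suggestion that this is merely a detail left for later. The protocol states a selection rule, and the rule is a poor one.

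**Conclusion.** The point holds for the logistic and linear regression models. Their baseline covariates are chosen by undefined chance imbalance, so a given prognostic variable would usually be absent: about 95% of trials at an assumed p < 0.05 and about 80% at p < 0.20.

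For a continuous outcome at 0.5 SD with 48 per arm and correlation 0.3 to 0.5, the cost is roughly 5 to 14 points of power (66% against 71% to 80%). It is smaller for binary success: 3 to 7 points with 48 per arm and 1 to 3 points with 25, in the first logistic simulation. It is about one point or less at the planned 0.8 SD. All of these rest on assumed correlations and effects.

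Overall type I error is not inflated and the primary analysis is untouched. The change is worth making because it costs nothing and gives a model that is known in advance.

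**What to change.** In the Statistical Analysis section, replace the phrase about variables unbalanced at baseline with a short named set of prognostic baseline covariates: for example initial Cobb angle and Risser stage or menarchal status, plus the stratification factors, which need to be named. State that the set is entered whatever the baseline table shows. Keep it small for the logistic model, because few subjects may have completed bracing within 3 years.

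State also that baseline tests are not used to choose covariates. Whether the baseline table shows p-values is then a reporting preference.

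Cost: wording only. Cobb angle, Risser stage and menarchal status are already established for eligibility, so no data, visits or subjects are added and the sample size does not change.

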This is a prospective randomized controlled trial investigating the therapeutic effect of the Hybrid Bracing Protocol(HyBP) over the Conventional Brace in enhancing In-brace Correction(IBC) for adolescent idiopathic scoliosis(AIS). Scoliosis is a complex three-dimensional spinal deformity and AIS is the commonest with a high prevalence of 2-4%. If left untreated, AIS can progress resulting in significant health problems including back degeneration and negative body images. Bracing, such as Underarm Brace(UAB) used in our center, is indicated for skeletally immature patients with Cobb angle $>20^{\circ}$. Another bracing system is a nighttime Lateral Bending Brace(LBB) designed in a bending position opposite to the convexity of the curve thus resulting in its overcorrection. If AIS becomes severe despite bracing, ultra-major surgery is indicated aiming at bony fusion of the deformed segment with instrumentation. It is therefore important to maximize treatment effectiveness with bracing to control curve progression and to avoid the need for surgery. In-brace Correction(IBC) is the percentage reduction in Cobb angle with bracing. Studies have reported IBC is an important determinant of brace effectiveness. For enhancement of IBC, we put forward the Hybrid Bracing Protocol(HyBP) combining the use of daytime UAB and nighttime LBB. To be best of our knowledge, HyBP has never been reported in the literature. Our pilot study on 8 patients treated with HyBP and 8 Cobb-matched historical controls treated with fulltime UAB showed very promising results with IBC of $42.1\pm22.0\%$ and $22.1\pm14.9\%$ in the HyBP and control group respectively. We therefore propose a formal prospective rater-blinded randomized controlled trial on 120 skeletally immature AIS female subjects with single thoracolumbar or lumbar curve newly prescribed with bracing. They are randomly allocated to the HyBP Group or the Conventional Brace Group (CB Group). The primary objective is to determine if the HyBP Group has better treatment effect in terms of In-brace Correction (IBC) when compared with the CB group at 3-month and 18-month after bracing. This is a 3-year study proposal representing the first phase of a project, to be followed by the second phase of the project when all subjects of the entire cohort will be assessed on curve outcome at time of completion of bracing and at 2 years post-bracing. This study will carry significant clinical impacts in that, if proven useful, the HyBP can be used for enhancement of treatment outcomes with bracing, thus preventing the scoliotic spine from deterioration and to avoid the need for surgery.

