1. The primary objective is to determine if the Hybrid Bracing Protocol (HyBP) combining the use of daytime Underarm Brace (UAB) and a nighttime Lateral Bending Brace has better treatment effect in terms of In-brace Correction (IBC) when compared with the conventional fulltime UAB
2. The secondary objectives are :
 - a. to determine if the HyBP has better treatment outcomes in terms of control of curve progression when compared with the conventional fulltime UAB for those who have completed bracing treatment or require surgery by the end of this 3-year study proposal
 - b. to determine if the HyBP has better outcomes when compared with the conventional fulltime UAB in terms of quality of life as assessed by SRS-22r, Spinal Appearance Questionnaire and the Brace Questionnaire

(b) (i)Research plan and methodology

Introduction :- To evaluate the usefulness of the HyBP, we propose a prospective randomized controlled study on 120 skeletally immature female AIS subjects newly prescribed with bracing. They will be randomly allocated to the Conventional Bracing Group (CB Group) or the HyBP Group. Brace treatment for both groups will last till skeletal maturity. Radiographic evaluation of curve severity and logging of brace compliance will be conducted according to standardized protocols at pre-scheduled intervals. Quality of life (QoL) will be assessed with questionnaires validated with local language for the local population. This is a 3-year study proposal representing the first phase of a project, to be followed by the second phase of the project beyond this current proposal when all subjects of the entire cohort will be assessed on curve outcome at time of completion of bracing and at 2 years post-bracing.

The flowchart for this 3-year study proposal is depicted in Figure 3.

Subject Recruitment:- Female subjects newly prescribed with bracing are recruited from our Scoliosis Clinic at Prince of Wales Hospital:

Inclusion criteria:-

1. Females with AIS diagnosed after detailed clinical and radiological evaluation by an experienced orthopaedic surgeon and
2. having a single lumbar or thoracolumbar curve with Cobb angle between 20° - 40° and
3. age 10 years and older when bracing is prescribed and
4. Risser 0 to 2 and
5. either pre-menarchal or less than 1 year post-menarchal and
6. with no prior treatment for scoliosis

Exclusion criteria [9]:-

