Other than treatment with different bracing protocols, the same standard orthotic and medical care for treating scoliosis will be provided for both the CB Group and HyBP Group according to the SOSORT “Standards of management of idiopathic scoliosis with corrective braces in everyday clinics and in clinical research” [23]. Subjects are instructed to wear the brace 23 hours daily [6]. The rest hour is for bathing and exercises. Brace compliance in terms of the average number of hours per day of brace wear will be separately evaluated for the daytime UAB and nighttime LBB.

Study Visits, Investigations and Measurements:-

1. ***Study visits:*** Subjects will be evaluated at baseline just before bracing, 3 months and 6 months after bracing and at 6-monthly intervals thereafter (Figure 3 for details).
2. ***Plain radiography of the whole spine in standing position*** will be taken with a standard protocol using the EOS system:
 - a. Measurements are made as follows
 - i. PA view for measurement of:
 - a. Frontal Cobb angle of the structural curve [24, 25].
 - b. Trunk Shift will be measured in cm indicating the perpendicular distance of mid-point of T1 vertebra from the central sacral line [24],
 - c. Curve levels, apex levels, side of curves
 - ii. Lateral view for measurement of Cobb angle for thoracic kyphosis and lumbar lordosis

- b. Timing
 - i. At baseline, 3rd month, 6th month, then every 6 months thereafter
 - a. PA and lateral x-ray are taken without brace for monitoring of curve severity
 - ii. At 3rd month, and 18th month
 - a. PA and lateral x-ray is taken without brace, then followed by taken with the daytime UAB for evaluation of In-brace Correction
 - iii. (At completion of brace fitting, a supine AP x-ray of whole spine taken with LBB will be assessed with the frontal Cobb angle)
- c. In-brace Correction (IBC) = $(([\text{Pre-brace Cobb}] - [\text{In-brace Cobb}]) / \text{Pre-brace Cobb}) \times 100\%$. It will be evaluated at the 3-month and 18-month time-points
- d. *Radiographic measurements will be done by a single experienced rater who is blinded to subject's grouping (he will not be shown the x-ray taken with the LBB).*
3. Brace compliance monitoring :- data on brace usage from the aforementioned monitoring devices will be retrieved at each study visit. The body temperature collected from the sensor will be used for compliance analysis and 32° Celsius is set as the compliance threshold [26].
4. Quality of Life (QoL) Questionnaires :-

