No similar study of this nature has been reported in the literature. According to our pilot study, the effect size is 1.065. Given the limitations with the pilot study as mentioned above, a more conservative and lower effect size of 0.8 will be adopted for sample size estimation. Assuming an alpha value of 0.025 and a statistical power of 0.95, 49 subjects are required for each group. Assuming a dropout rate of approximately 20% for each group, a total sample size of 120 subjects with 60 subjects in each group are required.

Figure 1A: The rigid underarm brace (Conventional Brace) used in this study

Figure 1B: Key pressure areas with paddings and the 3-point control system

In-brace Correction (IBC) with the Hybrid Bracing Protocol (HyBP)

Figure 2A: Before bracing

[figure not shown]
Figure 2B: x-ray taken with Lateral Bending Brace (LBB)

Figure 2C: x-ray taken with Underarm Brace (UAB)

Figure 3: Study flowchart

References

[2] Nachemson A. Adult scoliosis and back pain. *Spine*. 1979 Nov-Dec;4(6):513-7.

[3] Cobb JR. The problem of the primary curve. *Journal of Bone and Joint Surgery*. 1960 Dec;42-A:1413-25.

[4] Lonstein JE. Scoliosis: surgical versus nonsurgical treatment. *Clin Orthop Relat Res*. 2006 Feb;443:248-59.

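### The trial is sized at alpha 0.025 but judges its primary comparison at p < 0.05, with IBC tested at two time points and no rule that links the two levels

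*Protocol*

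**What the plan says.** All references are to the protocol.

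- **Statistical Analysis, test:** "For the primary objective, two-sided independent student's t-test will be used to compare between-group IBC".
- **Statistical Analysis, threshold:** "A p value of < 0.05 is considered statistically significant". No exception is made for the primary objective.
- **Sample size estimation:** "Assuming an alpha value of 0.025 and a statistical power of 0.95, 49 subjects are required for each group". The effect size is 0.8, set below the pilot value ("According to our pilot study, the effect size is 1.065"). The section gives neither the sidedness of the 0.025 nor a reason for it. With dropout, the target becomes 60 per group, 120 in total.
- **Opening summary:** the primary objective is the comparison of IBC "when compared with the CB group at 3-month and 18-month after bracing".
- **Study objectives (both listings):** the question is whether the hybrid protocol "has better treatment effect in terms of In-brace Correction (IBC) when compared with the conventional fulltime UAB", with no time point.
- **Study Visits, Investigations and Measurements, item 2c, on IBC:** "It will be evaluated at the 3-month and 18-month time-points".

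**The concern.** The sizing level and the decision level should be the same number on the same footing, and here they are 0.025 and 0.05. A one-sided 0.025 would equal a two-sided 0.05 and remove the conflict, so the first question is whether the stated 49 per group allows that reading.

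The second question is what the gap does. IBC is compared at two time points, and 0.025 is half of 0.05, which suggests a split over the two tests that was not carried into the analysis section. If a significant result at either visit were taken as success, two tests at 0.05 would not hold the overall error at 5%. The protocol neither states nor excludes that rule, so the threshold and the success rule could be settled after the results are known.

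**Working it through.** **Inputs.** Effect size d = 0.8, alpha 0.025, power 0.95 and 49 per group (Sample size estimation). Two-sided t-test and p < 0.05 (Statistical Analysis). Pilot IBC 42.1 ± 22.0 and 22.1 ± 14.9, 8 per group (Background, part C). The correlation between the 3- and 18-month tests is not given, so 0, 0.5, 0.8 and 0.9 are assumed.

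**1. Pilot effect size.** Pooled SD = √((22.0² + 14.9²)/2) = 18.79. Then (42.1 − 22.1)/18.79 = 1.064, against 1.065 stated. It reproduces.

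**2. The 49 per group.** Normal approximation: n = 2(z₁₋α/₂ + z₀.₉₅)²/d².
- Two-sided 0.025: 2(2.241 + 1.645)²/0.64 = 47.2, so 48.
- Two-sided 0.05 or one-sided 0.025: 2(1.960 + 1.645)²/0.64 = 40.6, so 41.

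Exact noncentral t, with df = 2n − 2 and noncentrality d√(n/2):

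| Level | n per group | Power at 49 |
|---|---|---|
| Two-sided 0.025 | 49 (power 0.948 at 48) | 0.952 |
| Two-sided 0.05, or one-sided 0.025 | 42 | 0.975 |
| One-sided 0.05 | 35 | 0.989 |

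For the t-test, only two-sided 0.025 gives 49.

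**3. Overall error over two time points.** P(at least one significant) under no effect, from a bivariate normal. At correlation 0 this is 1 − 0.95² = 0.0975.

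| Assumed correlation | 0 | 0.5 | 0.8 | 0.9 |
|---|---|---|---|---|
| 0.05 each, two-sided error | 9.75% | 9.1% | 7.8% | 7.0% |
| 0.05 each, false claim for HyBP | 4.9% | 4.5% | 3.9% | 3.5% |
| 0.025 each, two-sided error | 4.9% | 4.7% | 4.0% | 3.6% |
| 0.025 each, false claim for HyBP | 2.5% | 2.3% | 2.0% | 1.8% |

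The nominal levels are 5% two-sided and 2.5% in favour of HyBP. If both time points had to be significant at 0.05, the error would be at most 5%.

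**4. In IBC points.** The smallest significant difference with 49 per group is t × √(2/49) × 18.79 on 96 df:
- two-sided 0.05: 1.985 × 0.2020 × 18.79 = 7.5 points;
- two-sided 0.025: 2.277 × 0.2020 × 18.79 = 8.6 points.

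An observed difference between these values is significant under the analysis section but not at the sizing level.

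**5. How often one test would fall in that gap.** P(0.025 < p < 0.05) with 49 per group is the difference between the two powers: 0.975 − 0.952 = 2.3% at d = 0.8. At an assumed true d of 0.4 or 0.5 it is about 11%.

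**The case against.** The strongest reply is that the sidedness of the 0.025 is unstated, and one reading makes the two levels agree. A one-sided 0.025 Mann-Whitney calculation at its minimum relative efficiency of 0.864 also gives 49 per group (power 0.953 at 49, 0.949 at 48). The pilot was analysed by Mann-Whitney, so this route is conceivable. It cannot be excluded, but it would mean that the trial was sized for a test other than the t-test named for the primary objective. Either way the two sections need reconciling.

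Other points on that side stand:
- Sizing at a stricter level than the one used for testing costs no power.
- The inflated error needs an either-time-point rule that the protocol never states. Only the opening summary ties the primary objective to both visits, and a success rule could be left to a statistical analysis plan.
- On the protocol's own effect size, the two thresholds would rarely give different answers: 2.3% with 49 per group.
- The 7.5 to 8.6 point band rests on an SD from two groups of 8.

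These limit the size of the problem but do not remove it. The protocol itself fixes both levels, and for the test it names they disagree.

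**Conclusion.** The concern holds and should be fixed. For the two-sided t-test named in the protocol, the sizing level (two-sided 0.025, 49 per group) is not the decision level (two-sided 0.05, which needs 42). That conclusion rests on the protocol's own effect size, power and test.

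The consequence for type I error is conditional. It reaches 7.0% to 9.75% two-sided under an either-time-point rule with the assumed correlations, and does not exceed 5% under a both-required rule. That 0.025 was meant as 0.05 split over the two visits is the simplest reading, but it is an inference; the protocol does not say so.

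**What to change.** **Statistical Analysis.** Replace the single threshold with wording such as: each of the two primary IBC comparisons (3 months and 18 months) is tested at two-sided 0.025; two-sided p < 0.05 applies to all other analyses.

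**Sample size estimation.** State that the 0.025 is two-sided and applies per time point. If the sponsor had another reason for 0.025, give it here and make the analysis section agree.

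**Alternative.** If the sponsor prefers a fixed sequence (3 months, then 18 months) or a both-required rule at two-sided 0.05, state it in Statistical Analysis and restate the sizing. At d = 0.8 at both visits, 49 per group then gives 97.5% power per test and roughly 95% to 97% for both together, depending on the correlation.

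**Cost.** The first option needs one sentence and one clause, with no change to the 120 subjects. Each primary test becomes stricter: with 49 per group and d = 0.8, power per time point is 95.2% instead of 97.5%, and the smallest significant difference is about 8.6 instead of 7.5 IBC points at the pilot SD.
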